Additionally, it is the hope of the research team that results of this study will benefit future patients and their physicians by providing more information regarding the use of CBD after surgery. This will allow for a more open and informed dialogue, and possibly a change standard of care treatment.

Drug Shipment, Storage, Dispensing, Accountability, and Destruction: The CBD and matching placebo ODTs will be shipped to the NYU Langone Health Research Pharmacy in bottles labeled CBD or Placebo 25mg ODT with the subject #, date of dispensing and # of ODTs. Subjects will be dispensed enough 25mg ODTs for a maximum dose of every 4-6 hours for 14 days (subjects weighing over 80kg will be dispensed twice the amount of ODTs to account for 2 ODTs per dose (a total of 50mg CBD or placebo per dose). Subjects will be reminded that they should take the CBD or placebo ODT orally, every 4-6 hours, as needed for 14 days. The dates and times the ODT is taken are to be recorded in the subject's diary. Subjects will need to bring the drug with them (including empty and unused bottles) to the site for their Day 7 and Day 14 visits for accountability. Any remaining drug will be collected at Day 14 and destroyed per NYULH Research Pharmacy SOP.

V. INVESTIGATOR'S QUALIFICATIONS AND EXPERIENCE

The CV, medical license, and human subjects' tutorial completion report are attached for all investigators who are participating in this study. All research personnel have medical research experience and are qualified to participate in this quality study. Most importantly, staff have been properly educated and certified with CITI training to conduct research in a matter that will maintain full patient confidentiality. The research coordinator for this study is trained in GCP

principles and practices and will be responsible for compliance with GCP guidelines for all study investigators and research assistants.

VI. SUBJECT IDENTIFICATION, RECRUITMENT AND CONSENT/ASSENT

Method of Subject Identification and Recruitment

Appropriate patients, who meet all of the inclusion criteria and none of the exclusion criteria, who require a shoulder arthroscopy, will be identified from the clinical offices of the investigator surgeons.

Process of Consent

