shoulder arthroscopy who receive post-operative CBD and a placebo group. Patients will be asked on postoperative Day 1, 2, 7, and 14 to rate their pain according to the VAS scale. Additionally, opioid consumption, CBD consumption, as well as patient satisfaction will be measured. Patients will be asked in the post-trial period to fill out a questionnaire pertaining to 1-year outcomes. The questionnaire will be in the form of a single online survey including ASES score, VAS score, KJOC Shoulder score, and SANE score.

Rationale for multi-center study:

The second site is essential for this project, for both recruitment and logistical purposes. While NYULOH does have high-volume, a large proportion of these patients will be ineligible due to the exclusion criteria and will not want to participate given that this is a randomized, controlled, double blinded study. Additionally, the second site PI was absolutely instrumental in the conceptualization and the design of this study, as well as securing the necessary funding for it happen. This study would not be feasible without their collaboration. Additionally, the second site PI has an academic appointment here at NYU Langone, and is instrumental in the education of the trainees here at our institution

Primary Objective

The primary objective of the study is to determine if there are any differences in post-operative pain between patients receiving CBD after shoulder arthroscopy compared to patients who do not receive it.

Secondary Objective

Secondary objective of the study is to determine if there are any differences in patient satisfaction, the incidence of opioid induced nausea, and the numbers of opioids and CBD/placebo ODTs consumed by the two patient cohorts.

II. CHARACTERISTICS OF THE RESEARCH POPULATION

Number of Subjects

We will aim to enroll a total of 100 subjects (50 per cohort) as determined by the priori sample size calculator.

Gender of Subjects

Men and women will be included in this study.

Age of Subjects

Subjects included study will be aged 18-75 years, inclusive.

Racial and Ethnic Origin

There are no enrollment restrictions based on race or ethnic origin.

Inclusion Criteria

Patients will be screened for eligibility using the following criteria. All study subjects must meet the following inclusion criteria:

- Patients undergoing an arthroscopic shoulder procedure (rotator cuff repair, decompression, labrum repair)
- Patients ages 18-75, inclusive

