- Female patients must be currently practicing effective forms of two types of birth control, which are defined as those, alone or in combination, that result in a low failure rate (less than 1% per year) when used consistently and correctly
- Male patients must be using an effective form of contraception

Exclusion Criteria

Patients meeting the following criteria will be excluded from participation in this study:

- Legally incompetent or mentally impaired (e.g., minors, Alzheimer's subjects, dementia, etc.)
- Younger than 18 years of age
- Older than 75 years of age
- Any patient considered a vulnerable subject: pregnant women or fetuses, children, cognitively impaired adults, prisoners
- History of cannabis abuse or dependence
- History of coagulation abnormalities and thromboembolic disease or current abnormal coagulation test values
- History of stroke or acute coronary syndromes within 3 months before surgery
- Abnormal coagulation profile
- Renal failure (serum creatinine > 250 μ mol/L [2.83 mg/dL]) or liver cirrhosis
- Patients with a history of hypersensitivity to Percocet
- Patients that have been on pre-operative opioid management for any reason
- Patients meeting the DSM-V for major psychiatric illness, such as bipolar disorder
- Patients diagnosed with major depression, psychosis, or substance abuse disorder
- Patients with current or a history of suicidal ideation
- Breastfeeding females
- Patients with clinically significant illness, including cardiovascular disorders
- Clinically significant lab abnormalities
- Abnormal LFTs
- Patients with major neurological disorders, such as dementia, Parkinson's disease, cognitive impairment, epilepsy, history of traumatic brain/head injury, or seizures
- Patients with moderate (Child-Pugh B) and severe hepatic impairment (Child-Pugh C).
- Patients taking moderate or strong inhibitors of CYP3A4 and CYP2C19 (listed below) concomitantly
- Patients taking strong CYP3A4 and CYP2C19 inducers (listed below) concomitantly
- Patients taking substrates of UTG1A9, UTGB17, CYP2A1, CYP2B6, CYP2C8, CYP2C9 and CYP2C19 (listed below) concomitantly

| | |
|--------------------------|--|
| CYP3A4 Strong Inhibitors | Clarithromycin, Telithromycin, Nefazodone, Itraconazole, Ketoconazole, Atazanavir, Darunavir, Indinavir, Lopinavir, Nelfinavir, Ritonavir, Saquinavir, Tipranavir. |
|--------------------------|--|

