The use of cannabidiol (CBD) in pain reduction and opioid use after shoulder arthroscopy. A Double-Blind, Randomized Control Study

Version 06/28/2022

| | |
|-----------------------------|--|
| CYP3A4 Moderate inhibitors | Amiodarone, Erythromycin, Fluconazole, Miconazole, Diltiazem, Verapamil, Delavirdine, Amprenavir, Fosamprenavir, Conivaptan |
| CYP2C19 Strong Inhibitors | Fluconazole |
| CYP2C19 Moderate Inhibitors | Amiodarone, Fluvoxamine, Miconazole, Oxandrolone, |
| CYP3A4 Inducers | Carbamazepine, Dexamethasone, Ethosuximide, Glucocorticoids, Griseofulvin, Phenytoin, Primidone, Progesterone, Rifabutin, Rifampin, Nafcillin, Nelfinavir, Nevirapine, Oxcarbazene, Phenobarbital, Phenylbutazone, St Johns Wort, Sulfadimidine, Sulfinpyrazone, Troglitazone |
| CYP2C19 Inducers | Carbamazepine, Enzalutamide, Rifampin |
| UTG1A9 Substrates | Regorafenib, Acetaminophen, Canagliflozin, Propacetamol, Sorafenib, Indomethacin, Entacapone, Etodolac, Irinotecan, Propofol, Mycophenolic acid, Sulfamethoxazole, Valproic acid, Haloperidol, Zileuton, Flurbiprofen, Ibuprofen, Lumiracoxib, Valdecoxib, Buprenorphine, Nateglinide, Seratrodast, Gavestinel, Ketobemidone, Ambrisentan, Troglitazone, Mycophenolate mofetil, Ezogabine, Tapentadol, Dabigatran etexilate, Oxazepam, Dapagliflozin, Topiroxostat, Enasidenib, Dolutegravir, Ertugliflozin, Artenimol, Fostamatinib, Glasdegib, Diclofenac, Labetalol, Ataluren, Naproxen, Vadimezan, Dexibuprofen, Gemfibrozil, Fenofibrate, Darolutamide, Phenytoin, Formoterol |
| UTGB17 Substrates | Formoterol, Losartan, Diclofenac, Etodolac, Flurbiprofen, Ibuprofen, Naproxen, Suprofen, Mitiglinide, Zaltoprofen, Ambrisentan, Troglitazone, Morphine, Indomethacin, Mycophenolate mofetil, Ezetimibe, Mycophenolic acid, Vadimezan, Epirubicin, Tapentadol, Pitavastatin, Silodosin, Zidovudine, Lovastatin, Simvastatin, Oxazepam, Carbamazepine, Codeine, Fluvastatin, Valproic acid, Dapagliflozin, Enasidenib, Nalmefene, Acemetacin, Ertugliflozin, Artenimol, Labetalol, Tamoxifen, Carvedilol, Ketorolac, Dabigatran etexilate, Dexibuprofen, Gemfibrozil, Anastrozole, Loxoprofen, Cenobamate |

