| CYP1A2 Substrates | Acetominaphen, Amitriptyline, Clomipramine, Clozapine, Cyclobenzaprine, Doxepin, Duloxetine, estradiol, Fluvoxamine, Haloperidol, Imipramine n-deme, mexiletine, nabumetone, Napqi, Naproxen, Olanzapine, Ondansetron, Phenacetin, Perfenidone, Propranolol, Riluzole, Ropivacaaine, Rucaparib, Tacrine, Theophylline, Tizanidine, Triamterene, Verapamil, Warfarin, Zileuton |
| CYP2B6 Substrates | Artemisinin, Bupropion, Cyclophosphamide, Efavirenz, Ifosfamide, Ketamine, Meperidine, Methadone, Nevirapine, Propafol, Selegine, Sorafenib, Tramadol, Velpatasvir |
| CYP2C8 Substrates | Amiodaquine, Cerivastatin, Paclitaxel, Repaglinide, Selexipag, Sorafenib, Torsemide |
| CYP2C9 Substrates | Amitriptyline, Capecitabine, Celecoxib, Clopidogrel, Diclofenac, Doxepin, Fluoxetine, Fluvoxamine, Glibenclamide, Glimepiride, Glipizide, Glyburide, Ibuprofen, Irbesartan, Lesinurad, Lornoxicam, Meloxicam, Nateglinide, Phenytoin-4-oh2, Piroxicam, Rosiglitazone, S-naproxen-nor, S-warfarin1, Suprofen, Tamoxifen, Tolbutamide, Tolbutamide1, Torsemide, Valproic Acid, Venlafaxine, Voriconazole, Zakirlukast |
| CYP2C19 Substrates | Amitriptyline, Atomoxetine, Brivaracetam, Carisoprodol, Chloramphenicol, Citaprolam, Clomipramine, Clopidogrel, Cyclophosphamide, Diazepam-nor, Doxepin, Escitalopram, Esomeprazole, Flibanserin, Hexobarbital, Imipramine-n-deme, Indomethacin, Labetalol, Lansoprazole, Moclobemide, Nelfinavir, Nilutamide, Omeprazole, Pantoprazole, Phenobarbitone, Phenytoin(o), Primidone, Progesterone, Proguanil, Propranolol, r-Methobarbital, r-Warfarin, s-Mephotoxin, Suvorexant, Teniposide, Venlafaxine, Vorconizole |

Vulnerable Subjects

We do not intend to enroll vulnerable subjects.

Subject withdrawal criteria.

Patients are free to withdraw of their own volition at any time from the study before or after surgery.

A subject may be withdrawn from the study at any time if the Investigator determines that an illness, injury, complication or adverse event requires immediate study removal, whether or not considered by the Investigator to be related to the study drug.

Subjects found to have elevated liver transaminase and/or bilirubin levels on Day 2, or Day 7 will be removed from the study.

III. METHODS AND PROCEDURES

Methods and Procedures

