Patients indicated and scheduled for a shoulder arthroscopy will be identified from faculty surgeon case logs at the NYU Langone Health, Langone Orthopedic Hospital Sports Medicine Division. After informed consent is obtained, a chart review of patients' medications and past medical histories will be performed based on their electronic medical records to identify any current pain medications or exclusion criteria. In order to maintain the blind, another surgeon not involved in the procedure will randomize the patient to one of two cohorts using REDCap. Both surgeons are members of the study team. The randomization will be block randomization, via a computer generator on RedCap.

- Cohort 1: CBD ODTs to be administered with routine post-operative pain management regimen
- Cohort 2: Will not receive CBD; but a visually indistinguishable placebo ODT instead.

The resident physician, physician assistant, anesthesiologist, surgeon and study team members will remain blinded. Additionally, all patients will receive a traditional upper extremity interscalene block as per routine.

Immediate post-operative management will not be affected by this study. All patients will receive a standardized regimen of Percocet for pain management, which is standard of care post-operative treatment. Patients will receive a standard dose of 5/325mg and be discharged with 30 tabs and will be instructed to take 1-2 tablets, as needed, every 4-6 hours.

Additionally, patients will be randomized into one of two cohorts. The first cohort will receive a 25mg CBD ODT, every 4-6 hours as needed, with instructions to take two CBD ODTs if they weigh more than 80 kg (total maximum of 50mg per dose every 4-6 hours as needed). Cohort 2 will receive the same instructions, but with the placebo ODT instead. The dose of 25mg for subjects weighing \geq 80kg and 50mg for subjects weighing more than 80kg was selected based on recommendations from the FDA.

The use of cannabidiol (CBD) in pain reduction and opioid use after shoulder arthroscopy. A Double-Blind, Randomized Control Study

Version 06/28/2022

All subjects will be required to refrain from use of THC, or other cannabis-related products for the duration of the study.

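### Listed interacting non-opioid drugs newly started during ODT use are neither recorded nor restricted in the protocol text, apart from a bar on additional prescribed acetaminophen

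*Combined protocol and SAP*

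**What the plan says.** **At entry.** The Exclusion Criteria (section II) rule out "Patients taking moderate or strong inhibitors of CYP3A4 and CYP2C19 (listed below) concomitantly". Two further bullets, worded the same way, cover strong inducers and substrates. Thirteen drug lists follow. Several listed drugs can be bought without a prescription:

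- acetaminophen, in the UTG1A9 list ("Regorafenib, Acetaminophen, Canagliflozin, Propacetamol") and again under CYP1A2;
- ibuprofen and naproxen, for example in the UTGB17 list ("Flurbiprofen, Ibuprofen, Naproxen, Suprofen");
- omeprazole, in the CYP2C19 substrate list ("Nilutamide, Omeprazole, Pantoprazole").

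The stated checks are also at entry. Section III, Methods and Procedures, describes a post-consent chart review of medications and "past medical histories will be performed based on their electronic medical records to identify any current pain medications or exclusion criteria". Section IV, Protection against Risks, adds screening for contraindications.

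**During dosing.** The ODT is taken as needed for 14 days (section on drug shipment, storage and dispensing). Two on-study drug bars are stated: cannabis products (section III) and additional prescribed acetaminophen (section IV). Section IV also says that the Percocet regimen sits comfortably under a 4 g daily acetaminophen threshold.

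**What is recorded.** Study Design says that "opioid consumption, CBD consumption, as well as patient satisfaction will be measured". Section III specifies Percocet tablets and the dates and times of ODT use. The Study Time Points table has no item for other medication on Days 1, 2, 7 or 14. The data items named under Adverse Event Reporting include no other-drug field. Starting a listed drug is not among the subject withdrawal criteria, which do include raised liver tests: "Subjects found to have elevated liver transaminase and/or bilirubin levels on Day 2, or Day 7 will be removed from the study".

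**The concern.** The exclusion deals with drugs a patient already takes. It does not clearly deal with a drug started on day 3 for pain, nausea or heartburn. A patient could follow every written instruction and begin a listed non-opioid drug while taking CBD, and nothing in the protocol text would restrict it or plan a record of it.

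Two things are at stake. The first is acetaminophen. Every patient already receives it in Percocet, only further prescribing is barred, and the protocol describes more room under 4 g than the maximum instructed dose leaves. The second is interpretation of the safety data. Liver tests and adverse events will be compared between CBD and placebo, and the causality grades ask the clinician to weigh other drugs. Without a routine record, listed-drug use cannot be set beside those results by arm, and exposure that was never collected cannot be recovered at analysis.

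Opioids are left out of this point. Percocet is counted, and the schedule's opioid-consumption item may also capture a substituted opioid.

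**Working it through.** **Inputs.** Percocet 5/325 mg, 1–2 tablets every 4–6 hours as needed, 30 tablets at discharge (section III). Threshold 4 g = 4,000 mg of acetaminophen a day (section IV). ODT period up to 14 days. Enrolment 100 (section II). The only outside assumption is the strength of an over-the-counter acetaminophen tablet, taken as 325 to 500 mg.

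**Step 1: the protocol's own statement about 4 g.** Daily acetaminophen = tablets per dose × (24 / interval in hours) × 325 mg. Room = 4,000 mg minus that dose. Days of supply = 30 / tablets per day.

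| Schedule | Tablets a day | Acetaminophen (mg/day) | Room (mg) | Days of supply |
|---|---|---|---|---|
| 2 every 4 h | 12 | 3,900 | 100 | 2.5 |
| 2 every 6 h | 8 | 2,600 | 1,400 | 3.75 |
| 1 every 4 h | 6 | 1,950 | 2,050 | 5 |
| 1 every 6 h | 4 | 1,300 | 2,700 | 7.5 |

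The statement fits the lower schedules. It does not fit the maximum instructed dose, which is 3,900 / 4,000 = 97.5% of the threshold.

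**Step 2: one added over-the-counter tablet at the maximum dose.** 3,900 + 325 = 4,225 mg; 3,900 + 500 = 4,400 mg. Any strength above 100 mg crosses 4 g. At 2 tablets every 6 hours it takes three 500 mg tablets (2,600 + 1,500 = 4,100 mg), and more at the lower schedules.

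**Step 3: how long each situation can last.** The 3.9 g schedule lasts at most 2.5 days on the supplied tablets. After a supply used round the clock runs out, between 14 − 7.5 = 6.5 and 14 − 2.5 = 11.5 days of ODT use could remain. On those days Percocet contributes no acetaminophen, so the whole 4 g is open. These two windows do not overlap and must not be combined. As-needed use can stretch the supply, and refills are not described.

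**Step 4: search for a rule or record reaching a new start.**

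| Place in the protocol | What it covers | Reaches a newly started listed non-opioid drug? |
|---|---|---|
| Exclusion Criteria, chart review, screening | Drugs taken at entry | Not clearly |
| Methods, cannabis bar | Products not on the lists | No |
| Protection against Risks | Additional prescribed acetaminophen | Prescriptions only |
| Withdrawal criteria | Illness, injury, complication, AE, liver tests, own choice | No |
| Study Time Points, diary text | Opioid and ODT use | No |
| AE data items | Description, onset, severity, relationship, resolution | Not named |

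The documents give no rate of use of other drugs, so no frequency or effect on any result is estimated.

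**The case against.** **The exclusion may already extend into dosing.** Taking a drug concomitantly can mean taking it together with the study drug. A new start would then be a deviation, and the principal investigator reviews deviations and compliance quarterly under the Data and Safety Monitoring Plan. This reading is possible. However, the bullets sit in an entry list, and no patient instruction, follow-up check or log carries them into the dosing period. Where the protocol wants an on-study bar, as with cannabis, it states one. Without a log, detection is not assured.

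**The lists are not a blanket bar on co-exposure.** A reader might infer that any listed drug taken with CBD defeats the design. The documents do not support that. Acetaminophen is listed, yet the protocol gives it to everyone as Percocet and accepts the overlap with a prescribing limit. Propofol, ropivacaine, dexamethasone, ketorolac and ondansetron are also listed and can be routine around surgery. This part of the objection stands.

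**The acetaminophen risk is short-lived.** A reader might carry the 3.9 g figure across the days after Percocet runs out. Step 3 shows that this is wrong. It also means that a ban on over-the-counter acetaminophen until the last ODT is not supported by the arithmetic.

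**Attribution is partly handled.** Raised liver tests remove the patient whatever the cause. Adverse events are asked about at each visit, and the grades already require the clinician to weigh other drugs for each event. What remains is exposure in patients without an event. It matters for a comparison by arm, not for judging an individual case.

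**The missing pages may contain it.** Case report forms, the diary form and consent pages are not in the text reviewed. A medication field or an over-the-counter warning could be there. This limits the claim but does not remove it.

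**Conclusion.** The point holds as a minor gap in the protocol text. Listed non-opioid drugs are addressed at entry. During up to 14 days of ODT use, new starts are neither recorded nor restricted, apart from additional prescribed acetaminophen.

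The one concrete size is the acetaminophen figure: 3.9 g a day at the maximum instructed dose, for at most 2.5 days on 30 tablets, with 0.1 g to spare. One over-the-counter tablet (any strength above 100 mg) on such a day exceeds 4 g. Lower round-the-clock schedules leave 1.4 to 2.7 g, and finished Percocet contributes nothing.

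A reader might go further and infer that the efficacy or liver results will be biased. The documents give no rate of use and no difference between arms, so that does not follow. Nor can one conclude that the trial keeps no such record at all, given the pages not shown. The conclusion rests on the instructed Percocet schedule, the stated 4 g threshold, and the absence of described refills.

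**What to change.** 1. At the existing Day 1, 2, 7 and 14 contacts, record the name and dates of any drug taken other than Percocet and the ODT. Tabulate listed-drug use by arm beside the liver-test and adverse-event tables.
2. Tell patients not to take over-the-counter acetaminophen on days they take Percocet, and to ask the study team before starting any other new drug until the last ODT.
3. In Protection against Risks, replace the statement that the regimen is far under the threshold with the actual maximum of 3.9 g a day.

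Record routine peri-operative drugs but do not bar them. State that taking a listed drug does not by itself remove a patient from the study or the analysis. If the case report forms or consent pages already contain a medication log or such an instruction, cite it in the protocol instead.

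**Cost.** A short entry at up to 4 × 100 = 400 patient-contacts, with more than one drug possible at each, plus one table. Patients carry a small burden in calling first. Asking first might slightly change the use of non-opioid pain relief, but the instruction is the same in both arms. No new visit is needed, and the sample size and primary analysis are unchanged.

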Information to be recorded pre-operatively includes age, sex, height, weight, BMI, and American Society of Anesthesiology (ASA) classification. As well as baseline levels of complete blood count (CBC), chemistry profile, liver enzymes, gamma glutamate transferase (GGT), electrocardiogram, urine analysis, 12-panel urine drug test, and a urine pregnancy test.

Intra-operative information will also be recorded, including operative time, procedure, number of anchors, and complications. Patients will subsequently be stratified in different subgroups based on the procedure performed.

Pain severity scores at rest will be assessed by use of a visual analog scale (VAS; 0 = no pain, 10 = worst pain imaginable) at 6, 24, and 48 hours as well as 7 days and 14 days after surgery.

Patients will record their satisfaction with their management, on a 0-10 scale, 24 hours, 2 days and 7 days, and 14 days after surgery.

Additionally, any nausea experienced by the patients will be recorded by use of a VAS (0 = no nausea, 10 = worst nausea imaginable) at 2 days, 7 days and 14 days after surgery.

Percocet consumption will be recorded at 24 hours, 2 days and 7 days, and 14 days after surgery. Additionally, subjects will be asked to record the dates and times of CBD consumption.

Liver function tests, consisting of the standard hepatic panel, and including serum transaminase and bilirubin levels will be administered for study purposes on Day 7 and Day 14 after surgery.

Incidence of CBD-related side effects will be noted. Time to discharge from the post-anesthesia care unit (PACU) and time to discharge from the hospital will be recorded. Patients will be in the study a duration of 14 days and will be asked to fill out one online survey at the 1-year mark to determine the long-term effects that may be associated with using CBD.

In order to maintain the blinding, all data, including pain severity scores, side effects, opioid and CBD consumption, will be collected by the resident physician or physician assistant. However, if needed, in the event of an emergency or SAE, the unblinded surgeon responsible for randomization will be able to confirm whether a subject has been assigned to receive CBD or placebo.

| Study Time Points | |
|------------------------|---|

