| Day 0 - Day of Surgery | Baseline suicidality assessment (C-SSRS), Record Pain (6hrs and 24 hrs), Record clinical data during surgery and post op including time to discharge from PACU and time to discharge from the hospital, monitor for AEs |
| Day 1 | Record Pain, Opioid consumption, CBD consumption, Satisfaction, monitor for AEs |

The use of cannabidiol (CBD) in pain reduction and opioid use after shoulder arthroscopy. A Double-Blind, Randomized Control Study

Version 06/28/2022

| | |
|-----------------------------------|--|
| Day 2 | Record Pain, Opioid consumption, CBD consumption, Satisfaction, Nausea, monitor for AEs |
| Day 7 - Standard of Care Visit 1 | Record Pain, Opioid consumption, CBD consumption, Satisfaction, Nausea, Liver Function Tests - Non-standard of care, C-SSRS, Drug accountability, monitor for AEs |
| Day 14 - Standard of Care Visit 2 | Record Pain, Opioid consumption, CBD consumption, Satisfaction, Nausea, monitor for AEs Liver Function Tests - Non-standard of care, C-SSRS, Drug accountability and review of completed subject diary, monitor for AEs |
| Month 12 – Post-Trial Survey | Record Pain; Complete ASES, KJOC Shoulder, and SANE assessment |

Data Analysis and Statistical Plan

Our power analysis was based on the literature of post-operative pain control following shoulder arthroscopy. Under the assumption of a VAS of 3 and 1.8 for the control and CBD respectively, with a SD of 2: Group sample sizes of 45 in each group would achieve 80% power to reject the null hypothesis of equal means when the population mean difference between Control and CBD is $\mu_1 - \mu_2 = 3.0 - 1.8 = 1.2$ with a standard deviation for both groups of 2.0 at a significance level (alpha) of 0.05 using a two-sided two-sample equal-variance t-test. Thus, to allow for a 5% drop-out at 14-day follow-up, 100 patients would be required to enroll.

For descriptive statistics, categorical values will be described by percentages, and continuous variables will be described by means with standard deviations. To compare primary and secondary outcomes, a T-Test will be performed, with a p-value of 0.05 set to determine statistical significance. Testing will be performed to determine whether sample distribution is normal; if not, non-parametric testing will be performed.

Analysis of the Primary Efficacy Endpoint(s)

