Planned safety monitoring during the duration of the study will include monitoring for liver function, laboratory abnormalities and suicidality assessments throughout the study and for follow-up visits. Liver function tests, including serum transaminase and bilirubin, will be obtained on Day 2, Day 7, and Day 14. Elevated liver transaminase and bilirubin levels will be grounds for immediate removal from the study. C-SSRS will be assessed at baseline, Day 7, and Day 14 by the surgeon. Although CBD does not increase risk of suicidal ideation and behavior, this is being done in accordance with FDA recommendation for clinical trials involving drugs with CNS activity. If subjects are found to pose a risk to themselves, standard institutional procedures will be followed to refer subjects for appropriate care, including emergency care if needed.

The maximum CBD dose given to any subject will be less than 2mg/kg/day, well below levels associated with any hepatic risk (Iffland & Grotenherman, 2017).

The use of cannabidiol (CBD) in pain reduction and opioid use after shoulder arthroscopy. A Double-Blind, Randomized Control Study

Version 06/28/2022

CBD was not deemed to increase the severity of Percocet's opioid toxicities, as they act on different pathways. There is a potential for CBD to work in the same C450 cytochrome pathway as the acetaminophen, and thus no additional acetaminophen is to be prescribed outside of this, which is well below the maximum prescribing threshold of 4g per day.

The patients will stay in the recovery unit until cleared for discharge by an anesthesiologist. They will be prohibited from driving or operating a motor vehicle for 2 hours following their first dose of the study drug.

Patients will be educated on the importance of keeping the study drug in a safe place at all times and ensure it is not accessible to anyone other than themselves.

Additionally, all patients will be de-identified and given a code. Information linking the patient codes to the participants' names and medical record numbers will be stored in a secure location separate from the medical information. Access to the information linking the linkage codes with participant identifiers shall be restricted.

Potential Benefits to the Subjects

Patients may experience less pain post-operatively, and may require less narcotics use, which has a steeper side-effect profile. However, these benefits cannot be guaranteed.

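### The removal rule and the safety section rely on a Day 2 liver test that the procedures and the schedule do not include

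*Combined protocol and SAP*

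**What the plan says.** Four places in the protocol bear on the days of liver testing or on removal for an abnormal result.

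- **Section II, Subject withdrawal criteria:** "Subjects found to have elevated liver transaminase and/or bilirubin levels on Day 2, or Day 7 will be removed from the study".
- **Section IV, Protection against Risks:** "Liver function tests, including serum transaminase and bilirubin, will be obtained on Day 2, Day 7, and Day 14". The next sentence adds a removal statement that names no day: "Elevated liver transaminase and bilirubin levels will be grounds for immediate removal from the study".
- **Section III, Methods and Procedures:** the hepatic panel "will be administered for study purposes on Day 7 and Day 14 after surgery".
- **Section III, Study Time Points table:** the Day 2 row reads "Record Pain, Opioid consumption, CBD consumption, Satisfaction, Nausea, monitor for AEs" and has no liver test. The Day 7 row does have one ("Satisfaction, Nausea, Liver Function Tests - Non-standard of care, C-SSRS, Drug accountability, monitor for AEs"), and so does the Day 14 row ("monitor for AEs Liver Function Tests - Non-standard of care, C-SSRS, Drug accountability and review of completed subject diary").

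The Data and Safety Monitoring Plan has liver results reviewed quarterly at both sites but sets no test days.

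**The concern.** The removal rule is an instruction, not an option, and it depends on a laboratory result. If no sample is drawn on Day 2, that part of the rule can never be triggered. Hepatic toxicity is listed in section IV as a rare risk of the study drug, and early liver testing is one of the stated protections against it.

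The trial has two sites. Staff who work from the Study Time Points table would not draw on Day 2. Staff who work from section IV would draw and would have to act on the result. Either practice departs from some current text of the protocol. The second-site monitoring plan makes that site's investigator responsible for compliance but does not say with which list of days.

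There is a possible secondary effect on the analysis. Patients who complete less than 80% of follow-up visits are left out, so the day on which a subject is removed can decide whether that subject is analysed.

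**Working it through.** The plan gives no figure to reproduce here. The check is a comparison of the four places, followed by simple counts.

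**Step 1. Days named in each place**

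| Place | Day 2 | Day 7 | Day 14 |
|---|---|---|---|
| Section II, removal rule | named | named | not named |
| Section IV, test days | yes | yes | yes |
| Section III, procedures text | no | yes | yes |
| Section III, Study Time Points | no | yes | yes |

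The first row lists removal days and the other three list test days. The three lists of test days agree on Days 7 and 14 and disagree only on Day 2. When the removal rule is added, Day 7 is the one day common to all four.

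**Step 2. Removal rule against the section III schedule**

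- Rule days {2, 7}, scheduled draws {7, 14}.
- Rule days with no scheduled draw: {2}, which is 1 of 2.
- Scheduled draws not named in the rule: {14}.

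**Step 3. Size of the gap in testing** (100 planned subjects, assuming all stay in to Day 14)

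- Section IV: 3 × 100 = 300 post-operative draws.
- Section III: 2 × 100 = 200.
- Difference: 300 − 200 = 100 draws. This is an upper limit, because early removals would reduce both totals.
- Delay to the first post-operative result: 7 − 2 = 5 days. As a share of the 14-day dosing period, that is 7/14 = 50% instead of 2/14 = 14%. Dosing is as needed, so these are shares of calendar time and not of drug exposure.

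**Step 4. Possible effect on who is analysed**

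The 80% rule does not say which visits count. Two readings are shown, assuming that the contact on the day of removal counts as completed and that nothing is collected afterwards.

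| Visits counted | Removed at Day 2 | Removed at Day 7 |
|---|---|---|
| Days 1, 2, 7, 14 | 2/4 = 50%, excluded | 3/4 = 75%, excluded |
| Five VAS times (6, 24, 48 hours; Days 7, 14) | 3/5 = 60%, excluded | 4/5 = 80%, kept |

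Under the second reading, a subject removed on a Day 2 result leaves the analysis, while one removed on a Day 7 result stays in. Under the first reading both leave.

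**Step 5. Is the mismatch an artefact?** The Day 2 row of the table is intact and shows no redaction, and all four texts are current protocol text. Day 2 appears in two separate sections and is absent from two other places, so a single typing slip is an unlikely explanation.

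**The case against.** The contradiction itself is hard to dispute. The case on the other side concerns how much it matters.

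- **The Day 2 rule fails only if section III governs.** That is correct. Under section IV the draw takes place and the rule works, so the failure is conditional. The documents do not settle the condition, and the schedule table is a natural place for site staff to look.
- **Other safeguards exist.** Abnormal liver tests, cirrhosis and Child-Pugh B or C impairment are exclusions, and liver enzymes are measured at baseline. Adverse events are monitored, the investigator may withdraw a subject at any time, and the site investigators hold a quarterly teleconference. Testing and removal at Day 7 are not in dispute. All of this stands and limits the risk, but none of it supplies a Day 2 result.
- **Day 14 is not a real conflict.** This largely stands. The protocol says "Patients will be in the study a duration of 14 days", and remaining drug is collected at Day 14, so leaving that day out of the removal rule may be deliberate. The section IV statement has no day limit and may be permissive. A clinically significant Day 14 abnormality would in any case be an adverse event and be followed. The point is minor.
- **The draw count measures workload, not harm, and nothing shows the sites acting differently.** Both are fair. Divergence between sites is a possibility that the text leaves open, not something observed. No effect on the primary endpoint, power or type I error has been shown, and the 80% link depends on an undefined visit count.
- **Day 2 may be leftover text.** It may be, since only Days 7 and 14 are labelled as visits. The protocol does not say so, and leftover text in a mandatory safety rule still has to be corrected.

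**Conclusion.** The concern holds, with high confidence in the contradiction itself. Two current places rely on a Day 2 liver test and two leave it out, with nothing to say which prevails. Where section III is followed, one of the two days in a mandatory removal rule cannot operate. The first post-operative result then comes five days later than section IV states, and up to 100 promised draws are not scheduled.

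This must be fixed, because it is a safety rule that staff cannot follow without departing from another part of the protocol. The number of subjects affected cannot be estimated: no rate of liver elevations is given. The effect on the analysis set is possible but depends on how follow-up visits are counted. The Day 14 difference is secondary.

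**What to change.** Reconcile the withdrawal criteria, the procedures text, the Study Time Points table and Protection against Risks to one list of liver-test days and one removal rule.

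- Every day named in the rule should appear as a draw in the table.
- The status of Day 14 under the rule should be stated.
- The rule should have one wording. Section II joins transaminase and bilirubin with *and/or*, section IV with *and*, and neither defines what counts as elevated.
- Both sites should work from the same list.

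Which days and which rule apply is for the sponsor's clinicians; none is proposed here.

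**Cost.** If Day 2 is not kept, the change is wording only, across the four places. If it is kept, the table gains the draw that section IV already promises, up to one more per subject (up to 100 in all). That may also need an in-person contact at both sites, because the table and the drug accountability paragraph label only Days 7 and 14 as visits.
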